13.2 Analysis Populations

The safety population will include all patients who receive any amount of Investigational product (Lorelco TM or placebo). The safety population will be used for all safety analyses.

The efficacy evaluable population will include all patients who receive any amount of LorelcoTM and who have completed a post-baseline disease response assessment. The efficacy evaluable population will be used for all efficacy analyses.

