6 STUDY DESIGN

6.1 Design Type and Description

This is a Phase 2, randomised, double blind, placebo-controlled parallel group study in adults with mild to moderate AD.

The study will assess the efficacy, safety and tolerability of the treatment of Alzheimer's disease in approximately 300 subjects with LorelcoTM.

After consenting to participate in the study, screening procedures will occur between Days - 24 and -1. All subjects must have measurable mild or moderate Alzheimer's disease, and accordingly screening procedures will include:

- o A positive amyloid biomarker (PET scan) indicative of AD pathology,
- o Mini-mental-state examination (MMSE) score of 22 or greater,
- Free and cued selective reminding test (FCSRT) cueing index of 0.79 or less OR free recall score ≤17
- o Clinical Dementia Rating (CDR) global score of 0.5 or 1.0.
- o A study partner (partner/spouse/carer) consents to the minimum requirements:
 - Study partner will attend at least one screening visit
 - Study partner will be available via phone or in person to provide information to the study as required

Eligible subjects will be randomized in a 1:1 (active:placebo) ratio and return to the study unit on Day 1.

The dosing schedule for subjects is shown in Table 2. The two week initial placebo period will allow for implementation and retraining to assist with dose compliance, without giving participants the intervention drug. The dose level and regime begins at 250 mg a day (Week 3) to monitor for gastrointestinal safety events.

Table 2. Planned Subject Dosing Schedule

Week	Dose Level	Total Daily Lorelco TM Dose (mg)
Week 1 and 2	1 x placebo taken in the morning, with food.	0 mg
Week 3	1 x 250 mg Lorelco [™] (or matching placebo) taken in the morning, with food.	250 mg (or placebo 0 mg)
Week 4 -104	 1 x 250 mg probucol (or matching placebo) taken in the morning, with food. 1 x 250 mg probucol (or matching placebo) taken in the evening, with food. 	500 mg (or placebo 0 mg)

Subjects will self-administer LorelcoTM or placebo in the clinic under the supervision of site staff on Days 1 (±2 days) on Weeks 1, 2, 3, 4, 5, 15, 26, 39, 52, 65, 78 and 104. All other doses will be self-administered at home, or under the supervision of the designated study partner as appropriate. LorelcoTM and Placebo will be provided in a Webster pack or equivalent to assist with dose compliance.

[figure not shown]

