13.1 Sample Size Considerations

Estimated sample sizes are calculated for the two primary outcome measurements: ADAS-Cog and GM atrophy (hippocampal). In order to ensure that the study has sufficient power to detect differences in both of the primary outcomes, the sample size chosen is the maximum of that calculated for each primary outcome.

The primary analysis was an intention-to-treat analysis and included all randomized participants. Data will be analysed using both Generalised Estimating Equations (GEE) and Bayesian Analysis.

The analysis of primary endpoints will use linear mixed-effects models, with random slopes and intercepts. For the ADAS-Cog, using mixed model analysis published estimates from the ADNI cohort¹⁷ suggest a sample size of 125 AD participants per trial arm (total N = 250) will be required for power at 0.8 to detect a drug effect of 25% over two years and assuming a decline from baseline of 1.10 standardised units on the composite (SD change = 0.83).

Protocol Version 4, 06 OCT 2021

Confidential

Page 49 of 70

Curtin University Study Protocol
Protocol No.: PIA-2020

For the MRI markers, Ledig *et al.* reported the sample sizes required for a 25% intervention reduction over two years based on 322 patients with AD (with 117 followed for 24 months) and a reduction of 10.2% (6.2) for hippocampus¹⁸. Sample size calculations based on hippocampal volume suggest that 93 subjects per treatment arm are required (total N = 186).

Assuming a 20% attrition rate, a sample of 314 subjects will be recruited for the Cognitive study, and 233 subjects will be randomly chosen for the Imaging study.

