13.6 Efficacy Analyses

The primary analysis was an intention-to-treat analysis of all randomized participants. Data will be analysed using both Generalised Estimating Equations (GEE) and Bayesian Analysis. The analysis of primary endpoints will use linear mixed-effects models, with random slopes and intercepts.

The Alzheimer's Disease Assessment Scale's cognitive subscale (ADAS-Cog) is the standard primary cognitive outcome measure for evaluating treatments in clinical trials of mild-to-moderate AD. But the utility of ADAS-Cog is compromised primarily due to some of its items suffering from either floor or ceiling effects in different stages of AD. The current scoring methodology is also sensitive to missing item responses, scoring errors and variability in the administration of the ADAS-Cog, which are common in clinical trials.

The scoring methodology ADAS-Cog as proposed by Verma et al. will be utilised as it significantly improves the sensitivity of the ADAS-Cog in measuring progression of cognitive impairment in clinical trials focused in the mild-to-moderate AD stage²¹. This scoring methodology also provides a boost to the efficiency of clinical trials requiring fewer patients and shorter durations for investigating disease-modifying treatments. For patients with missing responses to certain items, this new scoring methodology does not require data imputation and estimates cognitive impairment using the set of items answered by the patients.

Analysis of all primary and secondary endpoints contrasting Probucol and placebo, after adjusting for covariates, will use mixed effects-regression with 'random' intercepts and slopes (as has been used for power calculations). Mean differences and associated 95% confidence intervals will be presented for the 'fixed' effect of Probucol treatment.

Further analysis investigating the relationship between change scores (post-minus pre-intervention scores) for the primary ADAS-Cog with MRI volumes (total GM, hippocampus, and medial temporal lobe volumes) and specific blood biomarkers (eg: plasma lipoprotein-Aβ) will be considered using Pearson (or Spearman where appropriate) correlation analysis. For all other correlations between recorded variables that lack an a priori hypothesis, control of statistical errors will be carried out using Holm-Sidak corrections for multiple comparisons.

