14.3 Case Report Form

An eCRF entry must be completed for each patient who is successfully enrolled (received at

Protocol Version 4, 06 OCT 2021

Confidential

Page 52 of 70

least one dose of study drug). For reasons of confidentiality, the name and initials of the patient should not appear in the eCRF. All eCRF entries, corrections, and alterations must be made by the investigator or other authorized study-site personnel.

Data entry into the eCRF will be conducted throughout study conduct according to the Sponsor's (or designee) instructions and reviewed by the Sponsor (or designee) to determine their acceptability. If necessary, eCRF queries will be raised by the Sponsor (or designee) relating to eCRF data entries. The Investigator or authorized study site staff must address all eCRF queries raised.

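### Section 13.2 assigns all efficacy analyses to a set that, as worded, contains no placebo patients and, even when patched, contradicts the stated intention-to-treat analysis

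*Protocol*

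**What the plan says.** Section 13.2 defines two populations. The safety population is "all patients who receive any amount of Investigational product (Lorelco TM or placebo"), so both products are named. The efficacy evaluable population, in the next paragraph, is "all patients who receive any amount of LorelcoTM and who have completed a post-baseline disease response assessment", with no mention of placebo. The section then states: "The efficacy evaluable population will be used for all efficacy analyses". It makes no exception for the primary analysis and defines no intention-to-treat set.

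Other sections describe a different set. Section 13.6 says "The primary analysis was an intention-to-treat analysis of all randomized participants", and section 13.1 says "The primary analysis was an intention-to-treat analysis and included all randomized participants". Section 7.1 and the efficacy part of the synopsis say the same. Section 13.6 also plans "Analysis of all primary and secondary endpoints contrasting Probucol and placebo, after adjusting for covariates", by mixed-effects regression. Section 6.1 sets the allocation: "Eligible subjects will be randomized in a 1:1 (active:placebo) ratio".

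Section 14.3 bears on whether an all-randomised set can be built: "An eCRF entry must be completed for each patient who is successfully enrolled", where enrolled is glossed as having received at least one dose of study drug.

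**The concern.** The trial's result is a between-arm difference, and the protocol fixes the patients who supply it in two incompatible ways. Under the literal wording of 13.2 the control arm is missing and there is no difference to estimate.

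Under the charitable wording, with placebo added, membership still depends on two things that happen after randomisation: taking study drug and reaching a post-baseline assessment. If the arms differ in who gets that far, the comparison no longer has the protection of randomisation. The protocol gives a reason to expect some difference. Section 4.4 reports significantly more QT-prolongation events on probucol than on control, and section 6.7 lists QTc change among the criteria for discontinuing dosing.

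An SAP author must contradict one section of the protocol whichever set is chosen. Because section 13 lets the SAP be finalised as late as database lock, the choice of primary analysis set could stay open until then.

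**Working it through.** 1. **The plan's own total.** Inputs are 125 per arm and 20% attrition (section 13.1) and 1:1 allocation (section 6.1). 125 / (1 − 0.20) = 156.25, rounded up to 157 per arm; 2 × 157 = 314. This reproduces the stated recruitment figure. For imaging, 186 / 0.80 = 232.5, rounded up to 233, which also reproduces. The 125 is taken as given, since this point depends on who is counted and not on how that number was obtained.

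2. **Section 13.2 read literally.** Placebo patients receive no Lorelco, so 0 of 157 qualify. At most 157 of 314 (50%) can enter any efficacy analysis, all from the active arm. The variance of a difference in means is σ²(1/n_active + 1/n_placebo). With n_placebo = 0 it is undefined and the contrast in section 13.6 cannot be estimated. The active arm is not complete either. Randomisation precedes dosing, and Table 2 gives placebo only in Weeks 1 and 2, so an active-arm patient who leaves in that period has taken no Lorelco and is excluded.

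3. **Section 13.2 with placebo added.** The conditions become (a) any dose of study drug, Lorelco or placebo, and (b) a completed post-baseline disease response assessment. Neither is implied by being randomised, so the set is still not the one named in the synopsis and in sections 7.1, 13.1 and 13.6.

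4. **When condition (b) can be met.** Section 11.6.2 and Appendix 1 place ADAS-Cog at baseline and Weeks 26, 52, 78 and 104. In Appendix 1 the first post-baseline DASS-21 and ADCS-MCI-ADL24 are also at Week 26. Imaging is repeated at Week 104, or at the last study visit for a patient who discontinues (section 6.1). The term disease response assessment is not defined anywhere in the protocol, so which of these counts is unclear.

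5. **How many could be affected.** The only attrition figure is 20%: 0.20 × 314 = 62.8, about 63. It covers the whole study and is not broken down by time. Losses before Week 26 therefore lie somewhere between 0 and about 63 under the planning assumption, and the protocol does not narrow that range.

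6. **The set stated elsewhere.** All randomised participants gives 157 + 157 = 314. The planned sample size does not change.

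**The case against.** The best reply is that nobody would analyse this trial without its control arm. The protocol often uses the brand name for blinded study drug: sections 8.5 and 9.1.1 speak of patients being given or taking Lorelco where placebo patients must be included. Section 13.6 demands a comparison with placebo, and intention-to-treat is stated four times. This stands as an account of intent, and the omission is probably a slip. It does not remove the need for correction. Section 13.2 itself names both products for safety one paragraph earlier, and the requirement for a post-baseline assessment remains in any case.

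A second reply is that section 13 calls itself a general framework and leaves detail to the SAP. That lowers the practical risk but does not reconcile two protocol statements.

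A third is that relabelling the set may change the estimate little. Section 13 rules out imputation, and a patient with only a baseline score adds almost nothing to a mixed-model treatment contrast. This is fair. Defining the set correctly settles who belongs in the analysis; it does not recover outcomes that were never measured.

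A reader might infer four stronger points that the documents do not support:
- **63 patients would be lost early.** The figure is whole-study attrition, and a patient who leaves after a Week 26 assessment stays in the set.
- **Everyone who leaves before Week 26 is dropped.** An early leaver in the imaging subset might qualify through a scan at the last visit, given the undefined term.
- **Gastrointestinal stops fall mainly on active drug.** The protocol says only that Week 3 dosing allows monitoring for such events and gives nothing by arm. The QT statement is the only arm-specific support.
- **Undosed patients leave no record.** Sections 14.1 and 14.2 require logs and source documents, and section 14.3 does not forbid an eCRF. What is missing is a requirement that they appear in the trial database.

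**Conclusion.** Wrong as written. The literal definition admits 0 of about 157 placebo patients, so the main comparison could not be estimated. The obvious repair of adding placebo still leaves a set that is not all randomised participants, in conflict with the synopsis and three sections of the protocol.

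The figure of 157 assumes that recruitment reaches 314 with 1:1 allocation. The effect of the repaired wording cannot be sized from the protocol, because the timing and arm split of losses are not given. Loss that differs by arm is foreseeable from sections 4.4 and 6.7 but is not quantified. The conclusion depends on none of these unknowns, since the contradiction lies in the text itself.

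**What to change.** In section 13.2:
- Define the intention-to-treat population as all randomised participants, analysed as randomised, and use it for the primary ADAS-Cog analysis and the other non-imaging efficacy endpoints.
- For imaging endpoints, use all randomised participants in the randomly chosen imaging subset (233 planned), as randomised. One all-randomised set cannot serve endpoints that are planned in only part of the sample.
- Keep any efficacy evaluable set as supportive only, defined identically in both arms (any study drug, Lorelco or placebo), and say which assessment qualifies a patient.
- Delete the sentence "The efficacy evaluable population will be used for all efficacy analyses".

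In section 14.3, require an eCRF for every randomised participant, so that the intention-to-treat set can be built from the trial database.

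The cost is a few sentences of protocol text and a small amount of extra data entry for randomised but undosed participants. The sample size and assessment schedule do not change.

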13.3 Demographic Data and Baseline Characteristics

Demographic data and baseline characteristics will be summarised using the safety population. Demographic data (including age, gender, race, ethnicity, body mass index, weight, and height) will be summarised using descriptive statistics. Medical history, surgical history, and prior medications will also be summarised.

13.4 Safety and Tolerability Analyses

Assessment of safety and tolerability is a seondary objective of the study. The analysis will assess the safety and tolerability of LorelcoTM in patients with mild to moderate AD using the safety population.

Safety and tolerability will be assessed through AE, clinical laboratory, vital signs, ECG, and physical examination data. AEs that occur at or after the first dose of Lorelco[™] or placebo will be classified as treatment-emergent adverse events (TEAEs).

The original terms used in the eCRF by Investigators to identify AEs will be coded by system organ class and preferred term using the current version of the Medical Dictionary for Regulatory Activities (MedDRA).

TEAEs will be grouped by system organ class and MedDRA preferred term and summarized by presenting the number and percentage of subjects who experience each TEAE and the number of TEAEs. Summaries by severity (graded according to the NCI-CTCAE v5.0 [or higher]) and relationship to Investigational Product will be provided for all TEAEs. Data listings will also be provided for any deaths, SAEs, and AEs leading to discontinuation of the study.

The actual values and changes from baseline at each post-baseline time point for clinical laboratory parameters, vital signs and ECG parameters will be summarized by visit and timepoint (where applicable). Where applicable, laboratory test results will be graded and summarized according to the NCI-CTCAE v5.0 (or higher). Baseline will be defined as the last assessment prior to the first dose of LorelcoTM/ placebo.

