4.4 Risk Assessment and Guidance for Investigators

Prolongation of the QT interval can occur in patients on probucol. Clinical trials by Yamashita¹⁰ and Kang¹¹ reported significantly more prolonged QT interval adverse events in individuals taking probucol (LorelcoTM), compared to controls. While drug-induced prolonged QT interval can be associated with significant adverse side effects such as ventricular arrhythmia (torsades de pointes), studies involving the use of 500 mg of Probucol daily, reported probucol-induced prolonged QT interval was not associated with, or increased the incidence of, ventricular arrhythmias. Furthermore, Walldius¹² reported that there was no significant difference in cardiovascular clinical events between individuals taking probucol and controls. No malignant arrhythmias or torsades de pointes were reported for either group. The absence of arrhythmias may be due to strict prolonged QT/QTc interval exclusion

Protocol Version 4, 06 OCT 2021

Confidential

Page 19 of 70

criteria. While there is no consensus on upper limit corrected QT/QTc interval values, many studies adopt an absolute QT/QTc interval prolongation of > 500ms. This reduces the risk of ventricular arrhythmia, as participants are discontinued prior to prolonged QT intervals associated with arrhythmia.

While QT prolongation by probucol may not enhance the occurrence of lethal ventricular arrhythmias, studies have identified several clinical risk factors for drug-induced arrhythmias, including probucol. These include;

- Cardiac factors (including congenital long QT syndrome, family history of sudden cardiac death, bradycardia)
- Myocardial hypertrophy
- Heart failure
- Liver disease
- Thyroid Dysfunction
- Renal or hepatic impairment

The above clinical risk factors should be considered prior to treatment with probucol¹³.

Further information regarding Lorelco $^{\text{TM}}$ is available in the Investigator's Brochure.

Protocol Version 4, 06 OCT 2021

Confidential

Page 20 of 70

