6.3 Duration of Follow-up

Patients removed from study for unacceptable AE(s) will be followed until resolution or stabilization of the AE(s). Otherwise, patients will have a final follow-up visit approximately 4 weeks after the last dose of study therapy.

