6.7 Dose Stopping Rules and Individual Dosage Adjustments

Dosing may be stopped or modified if suspected adverse drug reactions, changes in vital signs, ECGs, or clinical laboratory results are observed, and these changes pose a significant health risk. Of particular note for dose discontinuation are the following criteria;

- Corrected QT/QTc interval is in excess of 500 ms, or if it increases > 50 ms compared to baseline (baseline will be calculated as the mean of two time points, screening and baseline day 1).
- Occurrence of QT/QTc interval prolongation in association with symptoms of arrhythmia
- Subsequent prescription of a drug with potential QTc prolongation (Antimalarial; Macrolides; Quinolones; Triazole antifungals; Anti-arrhythmic; Antiemetic; Antidepressant; Antipsychotics)
- Evidence of Liver dysfunction, or primary biliary cirrhosis
- If for any reason the Investigator determines that continued participation in the trial is not in the participant's best interest.

The study may be terminated at any point in time at the discretion of the Sponsor.

Clinically or medically significant suspected adverse drug reactions, and SAEs considered to be related to study procedures will be followed until resolved or considered stable.

If an unscheduled interruption of treatment occurs, the PI should notify the Sponsor (via the Clinical Research Organization [CRO]) at the earliest possible time. A missed dose will not be made up. In the event that a patient requires an unscheduled interruption of treatment under conditions other than those associated with toxicity, the case will be reviewed by the PI and the MM, and discussed with the Sponsor/CRO to determine whether such a patient will be allowed to resume treatment.

At the discretion of the Investigator, a participant may be reinstated in the study 4 weeks after discontinuation of the participant. This will be evaluated on a case by case basis, and will also be reviewed by the DSMB. Participants will have a safety evaluation 4 weeks following study drug discontinuation.

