12.3 Procedures and Time Period for Detecting Adverse Events

The Investigator (or designee) is responsible for detection, recording and reporting of events that meet the criteria and definition of AEs.

As a consistent method of soliciting AEs, the participant shall be asked a non-leading question such as: "How do you feel?".

Detection and recording of study related AEs and SAEs extends from the signing of the consent form until completion of the last study related procedure (including follow-up for safety assessments).

Any AE reported or observed after the start of dosing with any study treatment until completion of the last study related procedure (includes follow-up for safety assessments) will be recorded as a treatment-emergent AE.

Any change in health status that is reported or observed after informed consent but prior to starting study treatment and is deemed by the study Investigator to be "not related" to study procedures, will be documented as medical history.

Any pre-existing conditions or signs and/or symptoms present in a patient prior to any involvement in the study (i.e., before informed consent) should be recorded as medical history. In addition, any change in health status, which is reported after informed consent but started prior to informed consent by the volunteer, will be documented as medical history.

Any worsening of a pre-existing condition that occurs following informed consent will be recorded as an AE.

A post-study AE/SAE is defined as any event that occurs outside of the nominal AE/SAE study detection period. Investigators are not obligated to actively seek AEs/SAEs in former study participants. However, if the Investigator learns of any SAE, including a death, at any time after a participant has completed the study and he/she considers the event reasonably

Protocol Version 4, 06 OCT 2021

Confidential

Page 45 of 70

	Study Protocol
Curtin University	Protocol No.: PIA-2020

related to the study treatment, the Investigator will promptly notify the Sponsor.

Patients must be provided with an "Emergency Wallet Card" indicating the name of the study treatment, the study number, the Investigator's name, and emergency contact number.

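### TEAEs are summarised per dosed patient with no allowance for time observed, so later-accruing harms on probucol can be understated if more probucol patients stop early

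*Protocol*

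**What the plan says.** Section 13.4 fixes the main adverse-event summary: TEAEs are coded by MedDRA and "summarized by presenting the number and percentage of subjects who experience each TEAE and the number of TEAEs". The synopsis repeats this. The denominator comes from section 13.2: "The safety population will include all patients who receive any amount of Investigational product".

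Sections 12.3 and 6.3 set the period in which an event can enter that summary. Under section 12.3, an event seen from the start of any study treatment "until completion of the last study related procedure (includes follow-up for safety assessments) will be recorded as a treatment-emergent AE". Under section 6.3, patients removed for unacceptable AEs are followed until those AEs resolve or stabilise; "Otherwise, patients will have a final follow-up visit approximately 4 weeks after the last dose of study therapy". Section 6.8 mentions a modified visit schedule for those who stop before Week 104, but the only visit it names is the one 4 weeks after stopping drug.

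Section 6.7 lists criteria of particular note for discontinuing dosing. They include "Corrected QT/QTc interval is in excess of 500 ms, or if it increases > 50 ms compared to baseline" and evidence of liver dysfunction. Section 4.4 says that two earlier trials "reported significantly more prolonged QT interval adverse events in individuals taking probucol" than in controls.

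**The concern.** A completer is under observation for new events to about Week 108. A patient who stops at Week 5 is under observation to about Week 9. Both count as one patient in the denominator. The unequal windows would not matter if stopping were unrelated to treatment, but the protocol ties discontinuation to an effect it expects more often on probucol. More early stopping on probucol would mean less observed time in that arm, and less observed time looks like fewer harms.

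Safety and tolerability is a secondary objective of a placebo-controlled trial whose results are meant to inform phase III. Events that build up over two years (falls, for example) are the ones exposed to the problem: a higher rate on probucol could look like parity.

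**Working it through.** **Inputs from the protocol.** Treatment to Week 104 and a final visit at Week 108; last visit about 4 weeks after the last dose for early stoppers (6.3, 6.8); 1:1 allocation (6.1); 20% attrition, not split by arm (7.1, 13.1).

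**Inputs that are assumptions.** The split of stopping by arm, its timing, the event rates and a constant hazard. The protocol gives none of these.

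**The plan's own figure on loss.** 125 / (1 − 0.20) = 156.25, rounded up to 157 per arm, gives 314. For imaging, 186 / 0.80 = 232.5, rounded up to 233. Both reproduce.

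**Observation windows, clock from Week 3 (start of randomised drug).**
- Completer: 108 − 3 = 105 weeks.
- Stopper, stopping uniform over Weeks 3 to 104: (104 − 3)/2 + 4 = 54.5 weeks on average.
- Stopper, stopping uniform over Weeks 3 to 26: (26 − 3)/2 + 4 = 15.5 weeks on average.

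Mean window per arm = (1 − d) × 105 + d × s, where d is the proportion stopping and s the stoppers' mean window. Each split below averages to the planned 20%.

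| Probucol v placebo | Timing | Probucol (weeks) | Placebo (weeks) | Ratio |
|---|---|---|---|---|
| 30% v 10% | spread | 0.70×105 + 0.30×54.5 = 89.85 | 0.90×105 + 0.10×54.5 = 99.95 | 0.899 |
| 30% v 10% | by Week 26 | 0.70×105 + 0.30×15.5 = 78.15 | 0.90×105 + 0.10×15.5 = 96.05 | 0.814 |
| 25% v 15% | spread | 0.75×105 + 0.25×54.5 = 92.4 | 0.85×105 + 0.15×54.5 = 97.4 | 0.948 |
| 25% v 15% | by Week 26 | 0.75×105 + 0.25×15.5 = 82.6 | 0.85×105 + 0.15×15.5 = 91.6 | 0.902 |
| 20% v 20% | same in both arms | equal | equal | 1.000 |

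**Event counts.** Count ratio shown = true rate ratio × window ratio. For a true 1.20 under 30% v 10%: 1.20 × 0.899 = 1.08 and 1.20 × 0.814 = 0.98.

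**Percentages.** Take an event with 20% risk over 105 weeks in both arms, so λ = −ln(0.80)/105 = 0.002125 per week. Averaging 1 − exp(−λw) over stoppers' windows gives 10.8% (w from 4 to 105) or 3.2% (w from 4 to 27). Under 30% v 10%:
- Spread: 0.70×20 + 0.30×10.8 = 17.2% v 0.90×20 + 0.10×10.8 = 19.1%.
- By Week 26: 0.70×20 + 0.30×3.2 = 15.0% v 0.90×20 + 0.10×3.2 = 18.3%.

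**Start of the clock.** Section 13.4 counts TEAEs from the first dose of Lorelco or placebo, which is Week 1. That adds 2 weeks to every window (107, 56.5 and 17.5). The 30% v 10% ratios become 91.85/101.95 = 0.901 and 80.15/98.05 = 0.817. The larger loss is then 18% rather than 19%, and the count ratios stay at 1.08 and 0.98.

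**Second model.** Give both arms 20% background stopping, uniform over Weeks 0 to 104, and give probucol an extra proportion x, either early (Weeks 3 to 15) or spread (Weeks 3 to 104). With a 108-week completer window, the placebo mean is 0.80×108 + 0.20×56 = 97.6 weeks. For x = 0.10 the probucol mean is 0.70×108 + 0.20×56 + 0.10×57.5 = 92.55 (spread, ratio 0.948) or 0.70×108 + 0.20×56 + 0.10×13 = 88.1 (early, ratio 0.903). Take an event with 20% placebo risk over the full window and a true hazard ratio of 1.5. The full-window risk ratio is (1 − 0.80^1.5)/0.20 = 1.42. The crude risk ratio is 1.42 with no extra stopping, 1.36 (spread) to 1.29 (early) at x = 0.10, and 1.22 to 1.02 at x = 0.30. The direction agrees with the first model.

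**The case against.** Section 13 calls itself a general framework and leaves detailed methods to a SAP that is not shown. That SAP may already add exposure-adjusted rates, so their absence from the protocol is not in itself a fault. This stands. What remains is that the protocol states a measure blind to observed time, in a design where it anticipates drug-related discontinuation.

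A reader might infer that harms are summarised only as raw percentages and counts. They are not: summaries by severity and relationship, listings of deaths, SAEs and AEs leading to discontinuation, and by-visit laboratory, vital-sign and ECG summaries (13.4) are planned, as are central-tendency and categorical QTc analyses (12.8). Excess stopping for AEs would therefore be visible. None of these outputs adjusts AE incidence for time observed.

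A reader might also infer that AE follow-up simply ends at 4 weeks. It does not: AEs behind a removal and other unresolved AEs are followed (6.3, 12.6), and an SAE the investigator learns of later and considers related is reported (12.3). Only active detection of new events closes. Nor are the triggering QTc or liver findings lost, since they occur before the window closes.

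Finally, unequal stopping is plausible but not shown. Section 6.7 says dosing may be stopped or modified, section 12.8 uses the thresholds in consideration of discontinuation, entry QTc limits apply, and reinstatement after 4 weeks is possible. The calculations ignore reinstatement.

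The alternative measures have weaknesses too. Person-year rates assume a roughly constant hazard, so for front-loaded events a shorter probucol window would inflate its rate. Time-to-event curves assume non-informative censoring, which drug-driven stopping may violate. That is why they belong beside n (%) and not in its place.

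**Conclusion.** The point holds as a conditional one. The crude TEAE comparison can understate later-accruing harms on probucol if more probucol patients stop early. The stronger reading, that it will understate them, is not supported, because the protocol gives no stopping rate by arm and equal stopping produces no bias.

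The illustrative size is a loss of observed time of about 10% to 19% at 30% versus 10%, and 5% to 10% at 25% versus 15%. It rests on assumed splits and timing and on a constant hazard. The upper figure needs all stopping, in both arms, to occur by Week 26. This is a cheap improvement to the safety analysis, not an error that invalidates it. Adjusting for time makes the comparison fairer but cannot recover new events that occur after detection closes.

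**What to change.** In section 13.4 and the synopsis, keep the n (%) and event-count tables and add:

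- person-years observed, by arm;
- for each TEAE, patients with a first event per 100 person-years at risk and events per 100 person-years, with time running from the first dose of Lorelco or placebo (the same start as the TEAE definition) to the end of each patient's AE window, and a between-arm rate difference or ratio with 95% CI;
- cumulative-incidence curves by arm for time to first SAE and to first QTc threshold event;
- a sentence stating that these are supportive to n (%), because rates assume a roughly constant hazard and drug-driven stopping may be informative censoring.

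The cost is a few sentences and some extra tables and figures. AE onset dates (12.4) and withdrawal or discontinuation dates (6.2) are already recorded in the eCRF, so no new visits, data or patients are needed. The downside is slightly longer safety output.
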